Randomised controlled trial of the clinical and cost-effectiveness of a contingency management intervention for reduction of cannabis use and of relapse in early psychosis (CIRCLE)

Final statistical analysis plan

Written by [name], [name], [name] and [name]

Final version 04/12/2017

Updated on 04/12/2017 to alter the exploratory analysis section

Updated on 27/11/2017 after further comment

Updated on 24/11/2017 to include health economic analysis

Updated on 09/11/2017 after a meeting with [name] (CI), [name] (Trial Manager), [name] (Lead statistician), [name] (Triallist), [name], [name] (Health Economists).

Updated on 12/06/2017 after comments from the TSC, [name] and [name]

Updated on 10/03/2016 after comments from [name]

Updated on 02/03/2016 after meeting [name] (CI), [name] (Trial Manager), [name] (Lead statistician), [name] (Triallist)

Updated on 11/2014 following review by the Trial Steering Committee

Updated on 17/10/2013 following comments from [name]

Updated 09/10/2013 after further clarifications from the Trial Management Group

Updated on 26/09/2013

Updated on 02/07/2013

Initial writing of the background 11/2012

Introduction

This analysis plan sets out the methods of analysing the predetermined primary and secondary outcomes of CIRCLE, which will be reported in the National Institute for Health Research, Health Technology Assessment report at the end of the trial and also in the main peer review paper to result from this randomised controlled trial.

The analysis of this trial will conform to the CONSORT statement¹⁻³ and the appropriate standard operating procedures written by Priment Clinical Trials Unit.

Further information on this trial can be found in the protocol version 6 (12/05/2014).

Trial summary

Aims

The aims of the main trial are to test whether the intervention results in an increase in time to relapse compared with the control group. Also to test whether the intervention results in a decrease in cannabis use and in positive psychotic symptoms and in an increase in participation in work or education compared with the control group.

Objectives

- To determine whether there is a difference in time to relapse in those randomised to the intervention compared with those randomised to optimised treatment as usual
- To investigate whether there is a difference in cannabis taking at follow-up between the randomised groups.
- To explore whether there is a difference in positive symptoms score at follow-up between the two randomised groups.
- To examine whether social functioning as defined by employment status is different between the two randomised groups.

Study population

Inclusion criteria

- Aged 18-36 years
- First episode psychosis and recent problematic cannabis use (having used cannabis at least once a week in more weeks than not over the previous six months)
- Being seen in the Early Intervention Service
- Having stable accommodation (not street homeless or roofless)
- Having sufficient command of English to give informed consent, to understand and answer the assessment instruments.

Diagnostic criteria for Early Intervention Service entry require a first psychotic episode significantly impairing functioning and lasting more than a week.

Exclusion criteria

- Not first episode psychosis
- Non-English speaking
- Currently engaged in substance misuse treatment with another agency
- Have unstable living arrangements
- Currently detained in hospital or prison, or on probation or Community Treatment Order requiring drug testing

Trial design

A single blind (assessors only) individually randomised controlled trial comparing contingency management to optimised treatment as usual. Initially this study was conducted in 11 Early Intervention Services (Camden and Islington, Hackney, Coventry, Tower Hamlets, Newham, north Warwickshire, south Warwickshire, Barnet, Enfield, Haringay, Kensington Chelsea and Westminster) as a pilot. This part of the study recruited 62 participants and aimed to obtain three month follow up on at least 60% of these. The full trial took place with those recruited to the pilot incorporated to the main trial and more sites from North London, South London, Heart of England, Surrey, Sussex MHRN Hubs. The main trial aimed to recruit 544 participants (including the 62 from the pilot trial). There were 42 Early Intervention Services (including the 11 that took part in the pilot) taking part in the trial. They aimed to recruit 13 on average per service.

The pilot trial recruitment ran from 01/06/2012 to 28/02/2013. The full trial, recruitment ran from 01/08/2013 until March 2016, with follow up ongoing until September 2017.

Randomised treatments

Intervention:

Contingency management involved offering rewards contingent initially on attendance and then on negative urinalysis results for cannabis. Following assignment to the contingency management group, participants were introduced to the voucher programme at an initial information and assessment session. Participants were informed that they needed to achieve two weeks of abstinence to return a cannabis free urine. In week 1 of the intervention, participants received a £5.00 voucher for attending and providing a urine specimen independent of the drug test results with the aim of familiarising participants with the urine testing and voucher procedures. From week 2 until week 12 participants earned vouchers contingent upon consecutive negative specimens or specimens that indicated a reduction in cannabis use.

If the participant has a pre-planned holiday or other significant commitment, they were able, on a maximum of two occasions, to suspend the intervention for one week, returning after 2 weeks rather than after 1 week. They were still be expected to show evidence of abstinence

at that point, and they needed to request this suspension no later than at the time of their previous scheduled appointment. The Early Intervention team was also be able to request suspension of the intervention for a maximum of one month if a participant relapsed and lost capacity to decide whether they wished to continue. If capacity was not regained in one month, the intervention was not continued.

Optimised treatment as usual (to be delivered to the intervention and control groups)

Optimised treatment as usual for cannabis was a phase specific, individually tailored, psycho-educational approach to problematic cannabis use for generic early intervention care coordinators that applies general psycho-educational approaches used in first episode psychosis⁴. The full delivery was typically achieved over approximately three hours, normally offered over regularly programmed sessions of 15-30 minutes duration.

Sample size

Assuming that 50% of the subjects in the control arm will not relapse during follow up,^{5 6} a 15% increase in this percentage due to intervention is clinically beneficial, and using a power of 90% and a significance level of 5%, a total sample size of 460 subjects will be required. This sample size is based on an analysis of time to relapse and will allow us to detect a 37% decrease in the hazard of relapse (hazard ratio of 0.63) in the intervention group using a Cox proportional hazards model. This sample size has been calculated using the Stata version 11⁷. The sample size is inflated by a factor of 1.06; assuming that the 120 care coordinators see an average of 4 service user participants in the trial and an intraclass correlation coefficient of 0.02, this gives a total sample size of 488. Finally, the sample size is inflated by 10% to account for drop outs (the primary outcome is obtainable from routine data), giving a total sample size of 544.

Randomisation

Participants were individually block randomised using blocks of size 2, 4 and 6 to either contingency management or optimised treatment as usual, stratified by severity of cannabis use (one to three times a week versus four or more times a week). Randomisation was carried out remotely and with impartiality by Sealed Envelope⁸.

Blinding

This was a single blind trial. Participants could not be blinded to their allocation as they will be participating in an interactive intervention. Outcome assessors were be blinded to allocation. However, this relied on participants, their care coordinators and clinical team not telling the assessors the.

The statisticians and health economists will remain blind to allocation until the primary analyses have been verified.

Outcomes

Primary Outcome

Time to relapse defined as admission to hospital, crisis house or crisis resolution team for mental health related problems. Data for this outcome were obtained from the informatics department of the relevant Trusts. This was in the form of the date of admission and which service admitted in the 18 months following baseline. Those that did not have any data recorded were assumed to not have any admissions and their data were censored 18 months after entry into the trial. If a participant died within the follow up period, the study team had this information and follow up will be censored at the date of death if they have did have a relapse before then. Likewise if their drop out date was known, this will be used as the date of censoring. Everything possible was done to trace people who dropped out to ensure that it was ascertained whether they had a relapse and if so when. This is because

drop out may be related to the outcome and therefore introducing informative censoring. [outcome type: time to event]

Secondary Outcomes

Secondary outcomes were measured at 12 weeks and 18 months. Analysis will be separately at these time points to match the clinical question of examining the outcomes at each of these time points rather than over time.

Cannabis positive urine sample at follow up. This will be a dichotomous outcome, positive versus negative.

Positive symptom score using the positive scale of the Positive and Negative Syndrome Scale (PANSS)⁹. This consists of seven items: Delusions, Conceptual disorganization, Hallucinatory behaviour, Excitement, Grandiosity, Suspiciousness and Hostility. Each item is scored on a scale from one to seven with one indicating absent and seven indicating extreme. These are summed to give an overall score which ranges from 7 to 49. [outcome type: continuous]

Negative symptom score using the negative scale of the PANSS. This consists of seven items: Blunted affect, Emotional withdrawal, Poor rapport, Passive-aphathetic social withdrawal, Difficulty in abstract thinking, Lack of spontaneity and flow of conversation, Stereotyped thinking. Each item is scored on a scale from one to seven with one indicating absent and seven indicating extreme. These are summed to give an overall score which ranges from 7 to 49. [outcome type: continuous]

Social functioning, based on self-reports regarding engagement in work or study, defined as any work (including sheltered or voluntary) or study (full or part time). [outcome type: dichotomous]

Number of days cannabis is used in the previous 12 weeks for follow up at 12 weeks and previous six months for 18 month follow up [outcome type: count]

Number of admissions over 18 months follow up. The primary analysis of this outcome will be operationalised to include those who provided a full 18 months follow up and those who died during follow up [outcome type: dependent on number of events. It may be possible to use this as count data else it will be dichotomised to none versus any]

Data collection

Data were collected at three time points, baseline, 12 weeks and 18 months post baseline.

Baseline

Demographic and social information (age, gender, ethnicity, social standing, living arrangements, employment, benefits received)

Clinical characteristics

Cannabis use using Time Line Follow Back¹⁰

Part E of the Structured Clinical Interview for DSM IV¹¹

Urine sample results

The Positive and Negative syndrome scales (PANSS)⁹

Employment status using questions from the Client Service Receipt Inventory (CSRI)

SF-12 (to be used in health economic analysis)^{13, 14}

EQ-5D (to be used in health economic analysis)

CSRI tailored to the study¹³ (primarily for health economic analysis)

12 weeks and 18 months

Urine sample results

Positive and Negative Syndrome Scale (PANSS)⁹
Engagement in work or study from the CSRI
SF-12 (to be used in health economic analysis)^{13,14}
EQ-5D (to be used in health economic analysis)
CSRI (to be used in health economic analysis)

18 months

Date of admission to hospital or crisis resolution team

Data entry

Data were entered using a web based system set up by Sealed Envelope⁸. This was set up so that, it mirrored the data collection sheets in order. It also had range checks, consistency checks and for closed questions gave a number of options plus “other” where appropriate. Assessors who entered the data will had no access to the group allocation through this system.

Data were checked by the statistician and health economists before analysis and any problems reported to the Trial Manager, who will rectify them as appropriate before data analysis.

Statistical analyses

The CONSORT¹⁻³ flow diagram will be constructed by/in collaboration with the Trial Manager who will have logs of service users who do and do not agree to take part in the study. It will include number of service users randomised to each arm of the trial, and the numbers who have follow up data available.

All analyses will be on an intention to treat basis and data from the pilot trial will be incorporated into the main trial.

Data will be analysed using Stata version 14¹⁵.

Descriptive statistics

Initial analyses will look at summary statistics for all variables, both overall and by randomised group. Summary statistics for continuous variables will be mean, median, SD, lower quartile, upper quartile, minimum and maximum and reported appropriately according to distribution. Summary statistics for categorical variables will be frequency and percentage within each category.

Summary statistics of baseline variables by whether a participant has dropped out of the study will also be examined to determine whether the drop outs had similar characteristics to those who remained in the study at baseline.

Analysis of the primary outcome

The primary outcome will be initially examined using Kaplan Meier survival curves by randomised allocation. If the assumptions of proportional hazards is satisfied, Cox Proportional Hazards modelling to compare the intervention and control groups will be carried out, adjusting for severity of cannabis use at baseline (the stratification variable, dichotomous – 1 to 3 times a week versus 4+ times a week) and whether the participant was part of the pilot trial. If the assumption of proportional hazards is not fulfilled, alternative modelling strategies will be employed. Robust standard errors will be used to account for clustering by therapist; which should account for most of the centre effects in this multicentre individually randomised trial. Hazard ratios and 95% confidence intervals will be presented.

Analysis of the secondary outcomes

These will be analysed separately for data collected at 12 weeks and 18 months. Models will include severity of cannabis use at baseline and whether the participant was part of the pilot trial. For the dichotomous outcomes (cannabis positive urine, engaged in work or study), logistic regression with robust standard errors to account for clustering by therapist will be used. If there are too few participants engaged in work or study for logistic regression to be possible then results will be reported descriptively. For continuous outcomes (positive and negative symptoms), linear regression with robust standard errors will be used.

For count outcomes, Poisson regression with robust standard errors will be used for count outcomes (number of cannabis days and number of admissions over follow up). If there are excess zeros for either count outcome, then the use of zero inflated Poisson regression will be explored.

Appropriate estimates and 95% confidence intervals will be presented for all analyses.

Missing data

There is not much missing data for the primary outcome since it is an objective outcome collected from the appropriate informatics departments.

There is missing data for other variables, especially at follow up. This may be because of non-attendance at the follow up appointment or non-response to specific questions. The extent and patterns of missingness will be assessed. Potential predictors of missing values that are related to the outcomes will be identified. .

Multiple imputation¹⁶ may be used if it is felt to be necessary. We will only impute outcome data if surrogate outcomes or variables closely related to the missing outcome(s) are available. Otherwise there is no gain in imputing outcomes¹⁷.

The primary analysis will be complete case analysis with analysis using multiple imputation being a supportive analysis if it is carried out.

Supportive analyses

There will be up to six supportive analyses for the primary outcome:

1. Analysis of all outcomes with their baseline predictors of missingness, that is modelling including the randomised allocation, whether the participant was in the pilot trial and the level of cannabis use at baseline
2. Analysis of the primary outcome excluding those participants who have no follow up secondary outcome data (for 12 weeks and 18 months separately) because those who drop out or die may be different to those who remain in the study and/ or survive. Before doing this, some demographic statistics comparing those who remained in the study and those who dropped out will be produced.
3. Analysis of those in the main trial only as some changes were made to the protocol at the end of the pilot before the main trial commenced, which might mean the participants behave differently to those in the pilot trial.
4. Analysis of the primary outcome controlling for the same factors as in the primary analysis plus the number of psychoeducation sessions attended (which is being offered in both arms of the trial).
5. Analysis of the primary outcome controlling for the same factors as the primary analysis and number of admissions in the six months prior to baseline.

6. Analysis of the primary outcome controlling for the same factors as the primary analysis, but using centre as the clustering variable not therapist.

There will be up to two supportive analyses for the number of admissions during follow up:

1. In addition to the factors included in the main analysis, this will include predictors of missingness.

2. Including those who were discharged within 18 months and assuming they had no admissions over the follow up time.

There may be supportive analyses for secondary outcomes collected at 18 months, as outlined in the missing data section.

Exploratory analysis:

We will investigate potential patterns and degree of non-compliance using clinical definitions of compliance and descriptive analysis. We will perform a Complier Average Causal Effect (CACE) analysis if feasible.

There are no subgroup analyses planned.

Health Economic analyses

The objective of the cost effectiveness analysis is to establish the relative cost-effectiveness of contingency management versus optimised treatment as usual at 18 months. The primary outcome will be QALYs (Quality Adjusted Life Years) calculated using EuroQol EQ-5D (3L) health profiles combined with health state preference values from the UK general populationⁱ. The resultant mean Quality of Life utility scores of the two treatment groups will be compared at eighteen months using unpaired *t*-tests. QALYs will be calculated using the area under the curve method and compared between groups adjusting for baseline EQ-5D utility scoresⁱⁱ.

Costs will be calculated based on resource use gathered from an adapted version of the client services receipt inventory (CSRI)ⁱⁱⁱ. The primary analysis will take an NHS and personal social services perspective^{iv}.

Costs of the contingency management intervention and optimised treatment as usual will be calculated using the salaries of staff delivering the intervention, plus employer on-costs, overhead costs, the cost of providers of supervision, and the cost of any equipment or consumables. A ratio of direct face-to-face to indirect non-face-to-face time will be applied.

Total costs at 18 months will be calculated by combining resource use with unit costs at 2016 prices. Unit costs will be derived from PSSRU and NHS reference costs. Medications will be costed using NHS prescription cost analysis data. Costs and QALYs will be discounted at 3.5% per year.

Costs will be compared, adjusting for baseline differences. Patient level costs and quality of life data will be bootstrapped with replacement (N = 10,000) to populate incremental cost effectiveness (ICER) planes, to estimate median cost-effectiveness and (pseudo) 95% confidence intervals. The probability of the intervention being cost-effective at different levels of willingness to pay for health benefits will be shown by generating cost-effectiveness acceptability curves (CEACs).

No subgroup health economics analyses are planned. The CHEERS statement will be completed^v.

Additional health economics analyses

1. Cost effectiveness at 3 months will be reported.
2. Results from a broader perspective including costs from criminal justice and cost of unpaid lost productivity due to illness will be reported.
3. Cost-effectiveness using alternative outcomes will be reported:
 - QALYs calculated using SF-12 data
 - Time to relapse (to 18 months)

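### A participant with no Trust record and no known drop-out date is counted as relapse-free for 18 months without a check that the records still covered them; the number-of-admissions analysis is stricter

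*SAP*

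**What the plan says.** SAP, Primary Outcome. On the source: "Data for this outcome were obtained from the informatics department of the relevant Trusts". On an empty return: "Those that did not have any data recorded were assumed to not have any admissions and their data were censored 18 months after entry". The paragraph then limits this rule. On drop-out: "Likewise if their drop out date was known, this will be used as the date of censoring". On death: "follow up will be censored at the date of death if they have did have a relapse before then". It adds that drop-outs were traced to find out whether and when they relapsed, because loss could be related to outcome.

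SAP, Secondary Outcomes, number of admissions. The main analysis is "operationalised to include those who provided a full 18 months follow up and those who died during follow up".

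SAP, Supportive analyses, second item for number of admissions: "Including those who were discharged within 18 months and assuming they had no admissions over the follow up time".

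SAP, Missing data: "There is not much missing data for the primary outcome since it is an objective outcome".

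**The concern.** An empty return can mean two things: the person was covered by the Trust's records for 18 months and was not admitted, or the records stopped covering them at some point. The SAP treats both as 18 months of observed, event-free time unless a death or drop-out date is known. It does not say whether discharge, transfer or moving away counts as drop-out.

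The document itself shows that the distinction matters. It expects some participants to be discharged within 18 months. For the count of admissions it will not assume in the main analysis that they had none. For time to relapse, which is built from closely related events, a similar assumption is the default whenever no drop-out date is known.

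Two things are at stake. The hazard ratio shifts if coverage is lost unequally between arms. The rule also hides the loss, because people who were not observed enter the data as complete. The statement that little primary outcome data is missing therefore cannot be checked from the data as coded.

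**Working it through.** **1. The plan's own figures.** Sample size section: 50% of controls relapse-free, 15 points more with intervention, 90% power, 5% significance (taken as two-sided), hazard ratio 0.63, N = 460.
- Exponential times: HR = ln 0.65 / ln 0.50 = 0.6215.
- Freedman: 10.507 × [(1 + 0.6215)/(1 − 0.6215)]² = 193 events. Mean event probability (0.50 + 0.35)/2 = 0.425, so N = 454.
- Schoenfeld at HR 0.63: 4 × 10.507/(ln 0.63)² = 197 events, so N = 464.
- Clustering: 1 + (4 − 1) × 0.02 = 1.06, and 460 × 1.06 = 488. Drop-out: 488/0.9 = 543, against 544 stated.

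These agree closely with the plan. No stated figure is wrong, and the same event rates are used below.

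**2. Assumptions.** The SAP gives no number of participants who lost coverage, so the share u in each arm is an assumption. Leaving is taken as uniform over 18 months and unrelated to relapse. No relapse is seen after leaving, and no drop-out date is known.

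**3. Events still seen.** With p the 18-month relapse probability and H = −ln(1 − p), a leaver's relapse is seen with probability 1 − p/H.
- Control: 1 − 0.50/0.6931 = 0.2787, so seen = 0.50 − 0.2213u.
- Intervention: 1 − 0.35/0.4308 = 0.1875, so seen = 0.35 − 0.1625u.

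A hand approximation to the hazard ratio under the SAP's rule is ln(1 − seen, intervention)/ln(1 − seen, control).
- 10% lost in each arm: ln(1 − 0.3338)/ln(1 − 0.4779) = 0.4062/0.6499 = 0.625.
- 10% control, 20% intervention: ln(1 − 0.3175)/ln(1 − 0.4779) = 0.3820/0.6499 = 0.588.
- 20% control, 10% intervention: ln(1 − 0.3338)/ln(1 − 0.4557) = 0.4062/0.6083 = 0.668.

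**4. Large-sample Cox estimate under the same assumptions.** Power is Schoenfeld's at 460, the plan's number before clustering and drop-out inflation. It is shown where the shift is towards 1 or absent.

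| Lost, control / intervention | HR, present rule | HR, censored on leaving | Power, present rule |
|---|---|---|---|
| 0 / 0 | 0.621 | 0.621 | 91% |
| 10% / 10% | 0.624 | 0.621 | 90% |
| 20% / 20% | 0.627 | 0.621 | 88% |
| 20% / 10% | 0.66 | 0.62 | 79% |
| 10% / 20% | 0.59 | 0.62 | – |

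With no true effect, 20% lost in the intervention arm against 10% in control gives HR 0.94, and the reverse gives 1.06.

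**5. When leaving is related to risk.** Assume no true effect and two halves of the sample with relative hazards 0.4 and 1.6. Only lower-risk people are discharged: 40% of the intervention arm and 20% of control.
- Censoring at discharge gives about 1.08 (0.92 with the arms reversed).
- The present rule gives about 0.94 (1.07 reversed) if records stop at discharge.
- The present rule gives 1.00 if Trust records continue after discharge.

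So censoring at discharge is not a safe replacement either. What decides it is whether the records still cover the person.

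**The case against.** The paragraph is more careful than its no-record sentence alone suggests. Known drop-out dates are used, drop-outs were traced, and informative censoring is named as a risk. Only untraced people with no known date are carried to 18 months. The stricter rule for number of admissions is partly explained by the outcome, since a count without an exposure term needs full follow-up. The second supportive analysis of the primary outcome drops participants with no secondary follow-up data, which touches lost coverage indirectly. All of this stands and limits the point. It does not supply a check that an empty return means observed, nor an analysis defined by record coverage.

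Some stronger readings are tempting, but the SAP does not support them:
- **Everyone discharged or moved away is carried to 18 months.** The known drop-out date rule may already censor some of them. The SAP does not say whether discharge counts as drop-out.
- **A discharged person can no longer appear in Trust records.** Someone discharged from the Early Intervention Service who stays in the area could still be admitted by the same Trust and recorded.
- **Relapses after leaving research interviews are discarded.** Drop-out is not defined as leaving interviews, and the tracing suggests that later relapses were sought.
- **The death sentence removes people who relapsed and then died.** It is garbled and plainly lacks the word *not*. This is editorial.

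**Conclusion.** The point holds as a fault in how the primary censoring date is fixed. A stated rule can count unobserved time as event-free, and it sits badly with the SAP's own handling of discharge for number of admissions.

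Its size depends on how far coverage loss differs between arms, which the documents do not report. A 10-point imbalance (10% against 20%) moves a true hazard ratio of 0.62 to about 0.59 or 0.66. Equal 10% loss leaves it at about 0.624 and costs one to two points of power. These figures assume uniform leaving unrelated to relapse and complete loss of records afterwards.

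A reader might infer that the trial's hazard ratio is biased, or that false positives are greatly inflated. The SAP does not support that: only the intervention arm has the 12-week voucher programme, but this does not establish a large difference in coverage over 18 months. Severity: should fix.

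**What to change.** Define the primary censoring date by record coverage:
- Count any relapse ascertained from records or tracing up to 18 months, including after drop-out from research assessments, unless permission to use records was withdrawn.
- Otherwise censor at the earliest of: the date the person left the area or the Trusts' records with no record from the receiving service; withdrawal of permission to use records; death; 18 months.
- Discharge from the Early Intervention Service alone does not censor someone who remains within the Trusts' record coverage.
- Credit 18 event-free months only where coverage is confirmed, and report the number with unconfirmed coverage by arm.
- Because censoring at discharge may itself be informative, run two sensitivity analyses: the present rule (no record means no relapse) and censoring at discharge.
- Correct the death sentence so that it applies to those who did not relapse before death.

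Cost: SAP wording, derivation of coverage dates and a little lost person-time. Discharge status is already needed for the number-of-admissions analyses.
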